4.3. Interim Analysis and Data Monitoring

No interim efficacy analyses or sample size re-estimations were conducted.

An external DSMB will be involved in the management of this study. The DSMB meeting will be held periodically for the duration of the study. The purpose of the DSMB is to review the progress of the study with special regard to safety and make recommendations to the Sponsor on how to handle any safety concerns that arise. Further details regarding the DSMB can be found in the DSMB charter which was finalized before the first meeting was scheduled.

5. Analysis Populations

The following analysis sets are planned for this study:

- **Intent-To-Treat (ITT) Analysis Set:** The ITT analysis set includes all randomized participants. The primary efficacy analysis will be based on this analysis set.
- **Intent-To-Treat (ITT-mild) Analysis Set:** The ITT-mild analysis set includes all randomized participants who have a baseline MMSE of 21-27.
- **Safety Analysis Set (SAF):** The SAF analysis set includes all participants who received at least one dose of study treatment. All safety analyses will be completed in the SAF analysis set and participants will be included in the group based on the treatment received.
- **PK sub-study Analysis Set:** The PK sub-study analysis set includes all participants who sign the PK consent and/or re-consent form and have at least one non-missing post baseline PK assessment available.

Assignment of participants to analysis sets will be confirmed at a blinded data review meeting to be held before the study database is locked.

6. General Issues for Statistical Analysis

6.1. Statistical Definitions and Algorithms

6.1.1. Baseline

The last observation recorded on or before the first dose of treatment will be used as the baseline observation for all calculations of change from baseline. In most cases, this will be the baseline visit (Day 1) pre-dose observation. In some cases, however, the baseline values may be obtained from the 60-day screening phase. For example, because MMSE is taken at screening but not at the baseline visit, the MMSE value obtained at screening will be used as the baseline value.

6.1.2. Adjustments for Covariates

Efficacy analyses will include as covariates the baseline value of the endpoint being analyzed and the MMSE baseline score, along with the interaction of these covariates with Visit. Investigative site (pooled, see section 6.1.6) will also be included as a categorical fixed effect.

6.1.3. Multiple Comparisons

The co-primary endpoints of ADAS-Cog12, and ADCS-ADL will each be tested at $p=0.05$ using the ITT analysis set. Multiplicity among secondary endpoints in the ITT analysis set will be controlled using a hierarchical, gatekeeping strategy. Secondary endpoints will be tested in the following order: iADRS, CDR-SB, ZBI, MMSE, and NPI-10. Testing will proceed in this order

until the first non-significant p value ($p > 0.05$). The first endpoint with $p > 0.05$ and all subsequent endpoints in the order will be declared non-significant, and all endpoints preceding the first non-significant test will be declared significant.

For the set of significant endpoints in the ITT analysis set, the corresponding endpoints in the mild subgroup (ITT-mild analysis set) will be tested. Testing for the mild cohort will proceed in the same order as for the secondary endpoints referenced above until the first non-significant p value. The first endpoint with $p > 0.05$ and all subsequent endpoints in the order will be declared non-significant, and all endpoints preceding the first non-significant test will be declared significant.

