11.3. STATISTICAL ANALYSIS

11.3.1 Primary Efficacy Analysis

Each of the two co-primary endpoints will be analyzed using a linear mixed model for repeated measurements. The dependent variable is the change from baseline and the model will include fixed effects for treatment group (two levels), week (5 levels, corresponding to Weeks 4, 16, 28, 40 and 52), the treatment group-by-week interaction, and the randomization stratification variable. The baseline value of the corresponding endpoint will be included as a covariate and the unstructured covariance model will be

used. The Baseline Visit (Study Day 1) ADAS-Cog12 and ADCS-ADL assessments will represent the baseline value for these variables.

For each of the two co-primary endpoints, the primary analysis will compare the 100 mg group and the placebo group at Week 52 using a two-sided test at the alpha = 0.05 level of significance. Study success requires that both co-primary comparisons are statistically significant.

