11.3.2 Secondary Analyses

The iADRS^{18,19} is a linear combination of scores from two well-established, widely accepted, therapeutically sensitive measures of AD: the ADAS-Cog and ADCS-iADL (the instrumental component of the ADCS-ADL). The iADRS has been validated and statistical properties of the composite performance have been described²⁰. All items of the ADAS-Cog12 and the ADCS-iADL will be included to generate this primary efficacy composite measurement without additional weighting.

Secondary clinical endpoint data (iADRS, NPI, MMSE, and ZBI) measured repeatedly will be analyzed using the same types of linear mixed models as described for the primary analysis.

Plasma assays may include P-tau181 and/or P-tau217, SavaDx and neurofilament light chain, and additional plasma biomarkers may be measured. All plasma biomarker data involving repeated measures will also be analyzed using the same types of linear mixed models as described for the primary analysis.

CDR-SB data will be analyzed using ANCOVA models with treatment group as a factor and the baseline value as a covariate.

All secondary analyses will be conducted using two-sided tests at the alpha = 0.05 level of significance, with no adjustments for multiplicity.

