8.1. Co-Primary Efficacy Analysis

Visit wise mean changes from baseline will be analyzed in the ITT analysis set using a restricted maximum likelihood (REML)-based repeated measures approach (MMRM). The MMRM analysis assumes a missing at random (MAR) missing-data mechanism, meaning that drop out is related to observed outcomes of the dependent variable and covariates, but not to the unobserved outcomes. The analysis will include the categorical, fixed effects of treatment group, visit, and pooled site, along with the continuous, fixed covariates of baseline value of the endpoint being analyzed (baseline), baseline MMSE score, and the interactions of treatment group, baseline, and baseline MMSE with visit. An unstructured (co)variance structure will be used to model the within-participant errors. If this analysis fails to converge, the following structures will be tested in this order, with the first structure yielding convergence to be used as the appropriate structure for that variable: heterogeneous Toeplitz, heterogeneous compound symmetric, and compound symmetric. If one of the structures other than unstructured is used, variance of the Maximum Likelihood Estimator (MLE) will be based on the Sandwich Estimator (empirical option in PROC MIXED statement). If none of the structures yield convergence, site will be removed from the model and the sequence of covariance structures will be refit as described above. The Kenward-Roger approximation will be used to estimate denominator degrees of freedom.

Significance tests for the between-treatment group differences will use a two-sided 0.05 level, with the primary analysis based on the ITT analysis set.

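### SAP 6.1.3 names a gatekeeping strategy but never makes the secondary test sequence conditional on both co-primary endpoints succeeding

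*SAP*

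**What the plan says.** SAP 6.1.3 (Multiple Comparisons) deals with the co-primaries first: ADAS-Cog12 and "ADCS-ADL will each be tested at $p=0.05$ using the ITT analysis set". SAP 8.1 adds the sidedness: "Significance tests for the between-treatment group differences will use a two-sided 0.05 level".

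Section 6.1.3 then turns to the secondaries: "Multiplicity among secondary endpoints in the ITT analysis set will be controlled using a hierarchical, gatekeeping strategy". The sequence is fixed: "Secondary endpoints will be tested in the following order: iADRS, CDR-SB, ZBI, MMSE, and NPI-10". Testing stops at the first secondary p-value above 0.05, and "all endpoints preceding the first non-significant test will be declared significant". A second paragraph of 6.1.3 takes the results into the mild subgroup: "For the set of significant endpoints in the ITT analysis set, the corresponding endpoints in the mild subgroup (ITT-mild analysis set) will be tested".

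The rule that both co-primaries must succeed is in Protocol 11.3.1: "Study success requires that both co-primary comparisons are statistically significant". There it defines study success and says nothing about secondary testing. Protocol 11.3.2 tests the secondaries at two-sided 0.05 "with no adjustments for multiplicity".

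**The concern.** A fixed sequence protects the claims inside it. It protects the trial as a whole only if entry to it depends on the primary result. Here the declaration rule takes secondary p-values as its only input, so iADRS and the endpoints after it can be declared significant when one or both co-primaries have missed.

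Two things are at stake. The first is which formal claims this registration trial may make if it fails its own success criterion. The second is the error rate over the co-primary claim and the ITT secondary claims together: each has its own 5%, and the plan does not link them.

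The choice of iADRS as first step makes the first issue practical. SAP 6.1.7 builds iADRS from ADAS-Cog12 and the instrumental items of ADCS-ADL, so a strong result on one co-primary can carry it when the other misses.

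**Working it through.** **1. The plan's own figure.** SAP 2.2 and Protocol 11.5 give a placebo change of 5.0 points, a 45% difference, SD 8.5, 300 per group, 90% power, two-sided 0.05 and 20% drop-out.
- Difference: 0.45 × 5.0 = 2.25 points.
- Standard error: 8.5 × √(2/300) = 0.694.
- Planned mean of the ADAS-Cog z-statistic: 2.25 / 0.694 = 3.24.
- Power: Φ(3.24 − 1.96) = 0.90. Enrolment: 300 / 0.80 = 375 per group.

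Both stated figures reproduce. The documents give no error rate for the co-primaries and secondaries taken together, so there is none to reproduce.

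**2. Is the entry condition written elsewhere?**
- SAP 8.1 and 8.2 give models and the 0.05 level, with no condition.
- SAP 4.2 refers to Section 6.1.2 for the type 1 error strategy, but 6.1.2 is the covariate section.
- Protocol 11.3.1 defines success only. Protocol 11.3.2 applies no multiplicity control at all.

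No place supplies it.

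**3. Error over the co-primary claim plus the ITT secondary sequence.** Assumptions not in the documents: normal test statistics with a common correlation ρ, and iADRS taken as the equal-weight standardised sum of the two co-primary statistics, (z₁ + z₂)/√(2 + 2ρ). Scenario: ADAS-Cog12 and CDR-SB effective, ADCS-ADL and ZBI null. An error is either a declared co-primary success (ADCS-ADL is null) or a declared ZBI effect reached through iADRS and CDR-SB. Simulated, two-sided 0.05:

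| Mean z of the effective endpoints | ρ = 0 | 0.3 | 0.5 | 0.7 |
|---|---|---|---|---|
| 3.24 (planned) | 7.2% | 6.5% | 5.9% | 4.9% |
| about 5 | 9.5% | 8.7% | 7.8% | 6.8% |

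A z of 5 means a difference of 5 × 0.694 = 3.47 points, or 3.47 / 5.0 = 69% of the placebo change, and power near 99.9%. It is not the design case. In the limit of a certain effect, with ZBI always reached, the error is 1 − 0.95² = 9.75% at ρ = 0 and 9.5% to 8.3% at ρ = 0.3 to 0.7. The general bound is 0.05 + 0.05 = 10%.

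With the entry condition, any false claim in this scenario requires ADCS-ADL to be falsely significant, so the error is at most 5%.

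**4. No effect on anything.** The chance that iADRS is declared is 5.0%. The chance of either a co-primary success or an iADRS declaration is also about 5.0%, because the two overlap. The entry condition would lower the iADRS chance to 0.5–1.7% (ρ = 0.3 to 0.7), but the 5.0% is not inflated.

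**5. How often iADRS would be declared in a failed trial.** These are not type 1 errors, because iADRS has a real effect in each case.
- *Only ADAS-Cog12 responds, at z = 3.24.* The iADRS mean is 3.24/√(2 + 2ρ): 2.01 at ρ = 0.3 and 1.76 at ρ = 0.7. iADRS is significant in 52.0% and 42.0% of trials. Subtracting the 2.5% in which both co-primaries succeed leaves 49.5% and 39.5%.
- *Both co-primaries at 90% power.* iADRS is significant in 98.0% and 94.0%, both co-primaries in 82.1% and 84.6%. The differences are 15.9% and 9.4%.
- *ADCS-ADL power lower.* The documents give a power basis for ADAS-Cog only. With ADCS-ADL power of 70% the range is 19–29%; with 50% it is 31–43%.

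**The case against.** The strongest reply is that the condition is implied. In ordinary usage, gatekeeping means that an earlier family controls entry to a later one; 6.1.3 treats the co-primaries first and the secondaries second; and SAP 4.2 says efficacy significance is judged in light of the type 1 error strategy. The authors may well have meant the co-primaries to guard the sequence. So a reader who infers that the SAP expressly permits secondary claims after failure goes too far: the text is silent. The silence still matters. The scope is written as multiplicity among the secondaries, and the next paragraph does write an entry condition for the mild subgroup while none is written for this step.

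A second reply is that the trial-level conclusion is safe, and that is correct. Protocol 11.3.1 defines success by the two co-primaries, and the SAP lists the protocol among its reference materials. A reader might infer that a good iADRS result could turn a failed study into a success; nothing in the documents allows that. What is exposed is the formal status of the secondary results.

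A third reply concerns size, and it also stands in part. Error near 10% needs effects well above the planned one; at the planned effect and a correlation of 0.7 there is no excess over 5%. The 40–50% and 9–16% figures might be read as false-positive rates, but they are true positives on iADRS. Whether such a claim should stand after a co-primary miss is a matter of claim policy, which the plan ought to settle in words.

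**Conclusion.** The gap is real on the text. The plan names a gatekeeping strategy, defines no entry condition, and lets secondary p-values alone decide secondary claims. The both-must-succeed rule is missing from the SAP.

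At the planned effect, error over the co-primary claim plus the ITT secondary sequence is about 7.2% to 4.9% for correlations from 0 to 0.7, against at most 5% with the condition. It rises to 9.5–6.8% at z about 5 and is bounded by 10%. Excess error needs a real effect on one co-primary; if nothing works, error stays near 5%. These figures rest on the assumed common correlation, the equal-weight form of iADRS and the chosen pattern of effective and null endpoints. They leave out the ITT-mild tests.

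That a failed trial could carry formal secondary claims follows from the written rule and needs none of those assumptions. This is an omission with a modest error cost at the design effect. It should be closed before unblinding, because a condition added later cannot be shown to have been planned.

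**What to change.** Add to SAP 6.1.3, in substance: the study succeeds only if both co-primary comparisons at Week 52 are significant at two-sided 0.05 in favour of simufilam; the secondary endpoints, and the ITT-mild tests that follow from them, are formally tested only in that case; otherwise all those p-values are nominal and no such endpoint is declared significant. The wording should cover ITT-mild explicitly, because entry there runs from whichever ITT endpoints were significant, which could be read to include a single winning co-primary.

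In the same edit, correct the SAP 4.2 cross-reference from 6.1.2 to 6.1.3. Also record in SAP Section 10, which now lists no changes, that the secondaries have moved from the protocol's unadjusted testing to a controlled sequence.

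The cost is a few sentences. The sample size stays at 300 evaluable and 375 enrolled per group. The sponsor gives up a formal iADRS claim when one co-primary misses. If the sponsor wants to keep that claim, the SAP should say so openly and state the error rate it accepts.

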3.2.1.2. Secondary Efficacy Endpoint(s) and Estimand(s)

The secondary efficacy endpoints of this study include the following:

- Mean change in the ADAS-Cog12 from baseline to Weeks 4, 16, 28 and 40
- Mean change in ADCS-ADL from baseline to Weeks 4, 16, 28 and 40
- Mean change in the iADRS (range 0 – 139, lower score indicates greater impairment) from baseline to Weeks 4, 16, 28, 40 and 52
- Mean change in the NPI-10 (range 0 – 120, higher score indicates greater impairment) from baseline to Weeks 28 and 52
- Mean change in the MMSE (range 0 – 30, lower score indicates greater impairment) from the screening visit to Weeks 28 and 52
- Mean change in the CDR-SB (range 0 – 18, higher score indicates greater impairment) from the screening visit to Week 52
- Mean change in the ZBI (range 0 – 88, higher score indicates greater caregiver burden) from baseline to Weeks 4, 16, 28, 40 and 52.

The estimands for the secondary efficacy endpoint(s) are similar to the co-primary estimands. Each secondary estimand has the following components:

Population	Participants with mild-to-moderate AD dementia who meet the study's inclusion and exclusion criteria.
Treatments	Simufilam 100 mg twice daily or placebo
Endpoints	ADAS-Cog12, ADCS-ADL, iADRS, NPI-10, MMSE, CDR-SB, ZBI
Summary Measure	Difference between treatments in LS mean change from baseline to the time points designated above
Intercurrent Events	All deviations from the intended dosing regimens and use of concomitant events medications will be handled consistently using a treatment policy strategy. Early study discontinuation will be consistently accounted for using a hypothetical strategy to estimate what would have been observed if the participant had not discontinued.

In addition, secondary estimands include the primary and secondary endpoints assessed in the population of participants with stage 4 AD. Stage 4 (mild) is defined as participants with baseline MMSE 21-27. Stage 4 and 5 represent all randomized participants.

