4.2. Introduction

Data processing, tabulation of descriptive statistics, calculation of inferential statistics, and graphical representations will use SAS (release 9.4 or higher). If the use of other software is required, the final clinical study report will specify the software that was used.

In general, summaries will be provided by study treatment group, unless otherwise noted. The column headings for the summaries will include the randomized treatment groups (Placebo BID, Simufilam 100 mg BID), unless otherwise noted.

Continuous (quantitative) variable summaries will include the number of participants with non-missing values (n), mean, 2-sided 95% confidence interval (CI), standard deviation (SD) and/or standard error (SE) if applicable, median, and minimum and maximum values.

Categorical (qualitative) variable summaries will include the frequency and percentage of participants who are in the category for each possible value. In general, the denominator for the percentage calculation will be based upon the total number of participants in the study population for the treatment groups (or cohorts) unless otherwise specified.

The minimum and maximum will be reported with the same degree of precision (i.e., the same number of decimal places) as the observed data. Measures of location (mean and median) and bounds of CIs will be reported to 1 degree of precision more than the observed data and measures of spread (SD and SE) will be reported to 2 degrees of precision more than the observed data. Percentages will be presented to 1 decimal place.

Statistical testing and inference methods for safety and efficacy analyses are described below. Efficacy results will be considered statistically significant after consideration of the strategy for controlling the Type 1 error as described in Section 6.1.2 of this SAP. Nominal p-values may be computed for other efficacy analyses as a measure of the association between the endpoint and the treatment effect rather than formal tests of hypotheses. Unless otherwise stated, all statistical tests will be conducted at the $\alpha = 0.05$ (two-sided) level, and a difference resulting in a p-value of ≤ 0.05 will be considered statistically significant. Corresponding 95% two-sided CIs will be presented for statistical tests.

All formal statistical comparisons will be based on LS means from the relevant contrasts in the mixed model for repeated measurements (MMRM) or analysis of covariance (ANCOVA).

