8.2. Secondary Efficacy Analysis

The iADRS, MMSE, NPI-10, and ZBI, in the ITT analysis set, and the ADAS-Cog12, ADCS-ADL, iADRS, MMSE, NPI-10, and ZBI, in the ITT-mild analysis set will be analyzed using the MMRM model as described for the primary analysis, with the exception for MMSE where the baseline value for the endpoint being analyzed is the MMSE baseline; therefore, the model for MMSE will include the categorical fixed effects of treatment group, Visit, and pooled site, along with the continuous, fixed covariate of baseline MMSE score and the interactions of treatment group and baseline MMSE with Visit.

The CDR-SB is only collected at Screening and Week 52. Therefore, the CDR-SB will be analyzed using ANCOVA with a model that includes treatment group, pooled site, and baseline MMSE. Plasma biomarkers will be analyzed with the MMRM analysis as described above.

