8.4. Subgroup Analyses of Efficacy Variables

The co-primary endpoints and iADRS will be analyzed by baseline severity, with subgroups defined as screening MMSE ≥ 21 and ≤ 27 versus MMSE < 21 . An additional subgroup analysis for the co-primary endpoints and the iADRS will use screening MMSE ≥ 20 and ≤ 27 versus

MMSE < 20. For these analyses, an MMRM model as previously described will be used, except that the model will have additional fixed effects for subgroup and its two-way interactions with treatment and Visit, and the 3-way subgroup-by-treatment-by-Visit interaction; and, baseline scores for the endpoint being analyzed and baseline MMSE and their interactions with Visit will be removed from the model due to their possible confounding with subgroup. Specifically, the analysis will include the categorical, fixed effects of treatment group, subgroup, pooled site, and Visit, along with the two-way interactions of treatment group with Visit and subgroup with Visit, and the three-way treatment group, subgroup, Visit interaction.

Similar models will be used to analyze subgroups by age (defined as < 65, 65-74 or ≥ 75), sex (defined as male or female), ethnicity (categories defined per FDA Guidance), ApoE4 genotype (defined as APOE4 non-carrier, carrier or homozygous) and medication use (cognitive enhancers, defined as yes or no).

There will be two additional subgroup analyses for the NPI-10. The first will include participants with a baseline NPI-10 score ≥ 2. The second will analyze the agitation/aggression domain scores in participants with a non-zero baseline score in that domain.

Note that there will be two sets of results for the mild subgroup. In section 8.2 the mild subgroup analyses are conducted by applying the primary analysis model to the ITT-mild analysis set. Those analyses are the primary means of drawing inference for the mild subgroup. The subgroup analyses described here for the mild / moderate subgroups are the primary means of drawing inference for differential efficacy between the subgroups. The analyses specified in section 8.2 are the primary means of understanding efficacy within the mild subgroup because that approach allows for including the same model as other secondary and primary endpoints.

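### SAP 6.1.3 runs the mild-subgroup tests as a second sequence at the full 0.05 beside the ITT secondaries and gives mild ADAS-Cog12 and ADCS-ADL no place in the order, so type 1 error is not held at 5% over everything it can declare significant

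*SAP*

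**What the plan says.** SAP 6.1.3 tests the two co-primaries at 0.05 in the ITT set and then says: "Multiplicity among secondary endpoints in the ITT analysis set will be controlled using a hierarchical, gatekeeping strategy". The ITT order is iADRS, CDR-SB, ZBI, MMSE, NPI-10, stopping at the first p above 0.05. It continues with the mild subgroup (baseline MMSE 21-27): "For the set of significant endpoints in the ITT analysis set, the corresponding endpoints in the mild subgroup (ITT-mild analysis set) will be tested". The order is given as follows: "Testing for the mild cohort will proceed in the same order as for the secondary endpoints referenced above until the first non-significant p value". The same 0.05 threshold decides which mild endpoints are declared significant or not.

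Other sections treat mild results as formal:

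- SAP 3.1.2 makes the co-primary and secondary endpoints in mild AD additional secondary objectives.
- SAP 3.2.1.2 states that "secondary estimands include the primary and secondary endpoints assessed in the population of participants with stage 4 AD".
- SAP 8.2 specifies that "ADAS-Cog12, ADCS-ADL, iADRS, MMSE, NPI-10, and ZBI, in the ITT-mild analysis set will be analyzed using the MMRM model".
- SAP 8.4 says of the Section 8.2 mild analyses: "Those analyses are the primary means of drawing inference for the mild subgroup".

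On the gate, Protocol 11.3.1 says: "Study success requires that both co-primary comparisons are statistically significant". SAP 4.2 says: "Efficacy results will be considered statistically significant after consideration of the strategy for controlling the Type 1 error as described in Section 6.1.2". Section 6.1.2 is the covariate section; the multiplicity rules are in 6.1.3. Protocol 11.3.2 planned no multiplicity adjustment for secondaries, so the SAP is already the stricter document.

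**The concern.** Two things are unsettled.

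**Alpha.** The mild sequence opens for any endpoint that succeeded in ITT, even when the ITT sequence has since stopped. If ITT iADRS succeeds and ITT CDR-SB fails, mild iADRS is still tested at 0.05. No alpha is split and no single order joins the two sequences. Success in ITT does not protect the mild test, because a real ITT effect can come entirely from the moderate stratum while the mild null is true.

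**Start.** The mild order is that of the secondaries, so it begins at iADRS. Mild ADAS-Cog12 and ADCS-ADL are in the set of claims but have no position in the order, and nothing says whether both are needed. Two competent statisticians could declare different mild results from the same data. This part needs no simulation.

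At stake is a registration study in which a formal ITT secondary claim and a formal mild claim could each have used its own 5% without the SAP saying so, and in which the order of the mild tests could be settled after the results are known.

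**Working it through.** **1. The plan's own power figure.** SAP 2.2 gives a placebo change of 5.0, SD 8.5, a 45% difference, 300 per arm and two-sided 0.05. The difference is 0.45 × 5.0 = 2.25. The mean Z is 2.25 / (8.5 × √(2/300)) = 2.25 / 0.694 = 3.24, and power is Φ(3.24 − 1.96) = 90%. With 20% dropout, 300/0.8 = 375. Both figures reproduce. The 90% is for ADAS-Cog alone in the whole ITT population. The SAP gives no figure for error over the family of claims.

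**2. Bound.** In one fixed sequence, a false rejection requires the first true null in the order to be rejected at 0.05, so each sequence alone holds 5%. With two side by side, the first true null of each can be tested at 0.05. If those tests were independent, the chance of at least one false rejection would be 1 − 0.95² = 9.75%.

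**3. Simulation of the 6.1.3 rules.** With mild share f, Z_ITT = √f · Z_mild + √(1−f) · Z_moderate, for seven endpoints, each tested two-sided at 0.05, with 300,000-400,000 draws per setting.

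- Assumptions not in the documents: f = 0.4-0.8; endpoint correlation 0.3-0.7; correlation of iADRS with each component 0.8.
- Secondaries are tested only if both ITT co-primaries succeed.
- True state: mild effect zero; ITT ADAS-Cog12, ADCS-ADL and iADRS effective through the moderate stratum; ITT CDR-SB onward null.
- Error: any false rejection among ITT secondaries or mild endpoints.

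| Mild start | 90% ITT power per gate endpoint | ITT power near 1 |
|---|---|---|
| iADRS first | 4.7-6.8% | 8.6-9.7% |
| ADAS-Cog12, then ADCS-ADL (ordered) | 4.8-6.9% | 8.6-9.7% |
| Both mild co-primaries at 0.05, no order | 7.1-10.4% | higher |
| Both mild co-primaries required first | 3.3-4.1% | 5.4-6.3% |
| ITT sequence alone, for comparison | 2.8-3.8% | 4.9-5.1% |

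Counting only false claims in favour of drug, an ordered start at 90% power gives 4.3-4.8%, against 2.4-2.5% for the ITT sequence alone.

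**4. What that state requires.** Take 804 × 0.8 / 2 ≈ 322 completers per arm. The standard error is 8.5 × √(2/322) = 0.670. With no mild effect, 90% ITT power needs a moderate-stratum benefit of 3.24 × 0.670 / (1−f), which is 3.6 points at f = 0.4, 5.4 at 0.6 and 10.9 at 0.8. The last two exceed the whole 5.0-point placebo decline.

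If the moderate stratum has only the planned 2.25 points, the mean ITT Z is (1−f) × 2.25 / 0.670, or 2.02 at f = 0.4 and 0.67 at f = 0.8. Joint error is then 1.2-4.3% with an iADRS start and 0.8-4.3% with the ordered co-primary start. Only unordered testing passes 5% (up to 6.2%, at f = 0.4-0.5).

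**5. Other states.**

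- Mild null, all ITT secondaries effective, 90% power, iADRS start: 2.5-3.3%, and at most 5% at any power.
- Equal effect in both strata: the mild tests add no error.
- Both mild co-primaries required, mild ADAS-Cog12 effective, mild ADCS-ADL null, the rest as in step 3: 4.6-6.4% at 90% power and 8.6-9.7% near power 1. Fixing the start without an alpha rule is therefore not enough.

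**6. Remedies.** A single sequence holds 5% by the argument in step 2 (worst simulated setting 5.08%, within simulation error). A split after the gate is bounded by 0.025 + 0.025 = 0.05 (worst setting 4.92%).

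**The case against.** The strongest reply is that nothing promised is broken. SAP 6.1.3 limits its control to ITT secondaries, the co-primaries decide study success, and each mild test already needs the same endpoint to succeed in ITT and stops at the first failure. Error above 5% with an ordered start needs a moderate-only benefit larger than the design effect, together with null later ITT secondaries. All of this stands, and it limits the size of the problem. It does not supply a start for the mild sequence or a statement that mild claims lie outside the error control.

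A reader might infer that the secondaries, and so the mild tests, can be reached after a failed co-primary. The documents do not support that. A gatekeeping strategy described directly after the co-primary tests, read with Protocol 11.3.1, makes the gate the natural reading, although 6.1.3 should say so. The reference in SAP 4.2 to 6.1.2 is a clerical slip. Neither point carries the concern.

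**Conclusion.** The concern holds in a limited form. As written, SAP 6.1.3 does not strongly control type 1 error over all the results it can declare significant, and it leaves the mild co-primaries without a position. The missing position and the missing link between the sequences are plain from the text. The size depends on the true state and on an assumed mild share and assumed correlations: about 5-7% for ordered starts in the state of step 3 at 90% ITT power, approaching 9.7% as power nears 1, and about 4.3% or less if the moderate-only effect is the planned 2.25 points.

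Three stronger readings go too far. First, the trial's main claim is not inflated: both co-primaries must succeed at 0.05. Second, absence of effect in mild AD does not by itself push error above 5%: with an iADRS start, a later ITT secondary must also be null. Third, 9.7% is not a general ceiling: it applies to ordered starts, and unordered testing of the mild co-primaries goes higher.

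**What to change.** Before unblinding, amend SAP 6.1.3 to state:

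- ITT secondaries are tested only if both ITT co-primaries are significant.
- In the mild block, ADAS-Cog12 and ADCS-ADL come first and both are required; the mild secondaries follow in the order already stated.
- The mild block has one pre-specified position in a single sequence after the co-primary gate, for example after ITT NPI-10, with testing stopped at the first failure. Mild p-values beyond a stop are nominal.

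There are two alternatives. One is to split alpha after the gate, 0.025 to the ITT secondaries and 0.025 to the mild block. The other, if no formal mild claim is intended, is to state that error control covers the ITT set only and to report mild results as supportive with nominal p-values. Correct the cross-reference in SAP 4.2 to 6.1.3 at the same time.

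No new data are needed. With one sequence, a formal mild claim is reached less often; with the split, both sequences run at lower alpha; with the last option there is no formal mild claim. SAP Section 1 says the study runs under a Special Protocol Assessment, so a change to the testing procedure should be checked against that agreement.
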